3.2 LAT8881

LAT8881 was initially developed for the treatment of obesity (known during these studies as AOD9604). Six clinical trials involving 936 subjects were completed, with over 700 subjects treated with oral LAT8881 (Section 3.2.2). There were no significant safety issues but the most recent efficacy study (METAOD006) did not meet the primary endpoint and development was discontinued for this indication in 2007.

3.2.1 Nonclinical studies

3.2.1.1 Preclinical pain studies

3.2.1.2 Nonclinical safety studies

Studies in rats and monkeys at doses up to 10 mg/kg LAT8881 intravenously for up to periods of 28 days had no clinically significant toxic effect in either species. Fourteen-day treatment with oral doses of LAT8881 up to 100 mg/kg/day was well tolerated in both rats and monkeys and without any overt systemic toxicity.

Chronic toxicity testing was conducted in both rodent and non-rodent species. Doses of 0 (control), 0.5, 20 and 100 mg/kg/day LAT8881 (0, 3.5, 140, 700 mg/m²/day) were administered orally to rats once per day for six months (26 weeks). There were no unscheduled deaths and no treatment-related clinical signs. No marked effects on body weight were observed and there were no treatment-related effects on food consumption, food conversion efficiency ratios, ophthalmic examination, organ weights, macropathology, histopathology or clinical laboratory parameters. There was no effect of LAT8881 on bone densitometry.

LAT8881 0.5, 10 and 50 mg/kg/day (6, 120 and 600 mg/m²/day) or vehicle control was administered to cynomolgus monkeys once per day for nine months. In this study there were no unscheduled deaths and no clinical signs attributable to treatment with LAT8881. There were no treatment-related changes in body weight, ophthalmology, haematology, biochemistry, urinalysis, organ weights, necropsy or histology. There was no effect of LAT8881 on bone densitometry.

No antibodies to LAT8881 were detected in the serum of rats and monkeys at the end of the toxicological studies, indicating that LAT8881 was not neutralised by an antibody reaction, and thus LAT8881 is considered unlikely to be immunogenic.

Extensive genotoxicity testing has been conducted. It is considered unlikely that LAT8881 is a potential genotoxic hazard to humans.

Reproductive studies have been undertaken in rats and rabbits at doses up to 50 mg/kg/day (rabbit) and 100 mg/kg/day (rat). The rabbit studies found no evidence of an effect on foetal development when administered from Days 6-18 of gestation. The rat studies involved dosing from 2 weeks pre-mating (males and females) up to Day 6 of lactation (females) or 2 weeks after pup delivery (males). No effect on reproduction was observed in these studies.

More detailed results from the preclinical studies with LAT8881 are provided in the Investigator's Brochure.

3.2.2 Clinical studies

Six clinical studies with LAT8881 have been completed, with over 700 subjects treated with LAT8881 (). These studies were designed to investigate the safety and tolerability of LAT8881 and subsequently its efficacy in the treatment of obesity (METAOD005, METAOD006).

In all studies it was noted that the study drug was well tolerated. The only dose-related adverse event (AE) trend was an increased incidence of gastrointestinal effects and general body symptoms of abdominal pain and headache in Study METAOD004 at 54 mg. This trend was not observed in subsequent studies.

More detailed results from these clinical studies with LAT8881 are available in the Investigator's Brochure.

4. Study objectives

4.1 Primary objective

 To evaluate the efficacy of oral LAT8881 in NP compared with placebo, when assessed by change in mean pain intensity scores from baseline to the end of four weeks treatment, based on an 11 point numeric pain rating scale (NPRS)

4.2 Secondary objectives

- To investigate the effect of oral LAT8881 in NP compared with placebo at different timepoints (up to 6 hours) following a single dose and after 4 weeks treatment, as measured by the NPRS (PK subjects only)
- To investigate the effect of oral LAT8881 on mean pain scores in NP compared with placebo after
 1, 2 and 3 weeks of dosing, as measured by the NPRS
- To determine the proportion of responders to oral LAT8881 in NP compared with placebo
- To investigate the maximum effect of oral LAT8881 in NP compared with placebo, as determined by the maximum change from mean NPRS baseline after 1, 2, 3 or 4 weeks treatment
- To evaluate the effect of oral LAT8881, compared with placebo, on functioning in subjects with NP when measured by the 7-item short form Brief Pain Inventory (BPI) Interference Scale
- To evaluate the effect of oral LAT8881, compared with placebo, on pain symptoms in subjects with NP when measured by the short-form McGill Pain Questionnaire 2 (SF-MPQ-2)
- To evaluate the effect of oral LAT8881, compared with placebo, on symptoms in subjects with NP,
 when measured by the Neuropathic Pain Symptom Inventory (NPSI)
- To evaluate the effect of oral LAT8881, compared with placebo, on emotional functioning when measured by the Beck Depression Inventory-II (BDI-II)
- To evaluate the effect of oral LAT8881, compared with placebo, on overall health and quality of life in subjects with NP, when measured by the Patient Global Impression of Change (PGIC) scale
- To determine the change from baseline in rescue medication use during oral LAT8881 administration, compared with placebo
- To evaluate the safety and tolerability of oral LAT8881 in NP after a single dose and after four weeks treatment
- To investigate the pharmacokinetics of twice daily oral LAT8881 in 15 subjects with NP after a single dose and after 4 weeks treatment with oral LAT8881

4.3 Exploratory objectives

- To investigate the relationship between baseline subject characteristics, such as clinical diagnosis (PHN or DPN)
 , and the change in NPRS after oral LAT8881 treatment, compared with placebo
- To investigate the relationship between plasma LAT8881 concentrations and the change in mean pain score in subjects with NP
- To investigate the impact of variability in NPRS scores during the first baseline period on the difference between baseline and 4 week NPRS scores after LAT8881 or placebo

5. Study design

5.1 Overall study design

This is a randomised, placebo-controlled, double-blind, crossover, multi-site, Phase IIa study to investigate the efficacy and safety of oral LAT8881 in neuropathic pain. The overall study design is shown in Figure 4. Details of the procedures during each phase are described in Section 8.

The pharmacokinetics (PK) of LAT8881 will be investigated on Days 1, 28, 50 and 77 in 15 subjects (PK subjects) at Australian sites. Quantitative sensory testing (QST) will be performed in up to 20 subjects (QST subjects) before the first dose on Days 1 and 50 and after the morning dose on Days 28 and 77. PK subjects will not participate in QST measurements and QST subjects will not participate in PK analyses.

[figure not shown]

Figure 4: Overall study design for LAT-NP-001

Potential subjects will be required to provide written informed consent prior to any study-specific screening procedures being performed. Screening assessments will be performed from Day -28 to Day -1. Subjects deemed likely to be eligible for the trial will be given access to a diary during Screening Stage 1 and training on how to complete it from Days -7 to -1 inclusive (Screening Stage 2, first baseline period). These diary results will be reviewed on Day 1 to confirm that the subject is eligible for the study.

On Day 1, after the first baseline period, eligible subjects will be enrolled and randomised to LAT8881 or placebo. They will receive the investigational medicinal product (IMP) twice daily for four weeks (Days 1 to 28). On the morning of Day 28 they will return to the clinic for their end of first treatment visit and will take an IMP capsule in the morning during their clinic visit. They will take their final IMP dose for this treatment period in the evening.

The first treatment period will be followed by a washout period of two weeks (Days 29 to 42 inclusive) and then a second baseline period of one week (Days 43 to 49 inclusive). Over these days (i.e. Days 29-49 inclusive) subjects will not take any IMP.

On Day 50, subjects will return to the clinic and cross over to receive the second treatment (either LAT8881 or placebo, whichever treatment was not received in the first treatment period) twice daily for four weeks (Days 50 to 77). On the morning of Day 77, they will return to the clinic for their end of second treatment visit and will take an IMP capsule in the morning during their clinic visit. They will take their final IMP dose for this treatment period in the evening.

Subjects will return to the clinic on Day 91, two weeks after their last treatment visit, for an end of study visit.

5.2 Justification of study design

This is the first study with LAT8881 in subjects with neuropathic pain. As such, it has been designed to evaluate, in a well-defined patient group, the concept that LAT8881 is safe and effective in this indication. Subsequent studies will evaluate other development issues, such as the optimal dosing strategy, and the

applicability of these results to related pain conditions.

Subjects enrolled into this study have been diagnosed with PHN or DPN, both conditions being well accepted examples of neuropathic pain. Because the pain is chronic, without a period effect, and treatment is symptomatic rather than curative, a crossover study is considered appropriate. Indeed, studies with other agents have successfully demonstrated analgesic effects in PHN and DPN with a crossover study design.⁷

A major advantage of a crossover design is the smaller number of subjects required to demonstrate efficacy, compared with a parallel design. In this study, 44 evaluable subjects are required to show the same statistical outcomes, compared with over 100 subjects had a parallel group design been utilised. The main disadvantage is the longer duration of the study for each subject and a higher risk of dropouts. It is anticipated that approximately 20% of subjects will not complete the study, based on analysis of Phase III studies with duloxetine, pregabalin and gabapentin in DPN and PHN⁸ and taking into account the good tolerability of LAT8881 in previous clinical studies. In an attempt to minimise dropouts in this study, subjects are allowed to continue on their current stable medications and will have access to rescue paracetamol. Should these measures not be adequate and the dropout rate is higher than anticipated, enrolment will continue until the required number of completing subjects is reached.

A four week treatment period is considered to be an appropriate balance between reducing the potential for dropouts and ensuring that there is adequate time to observe a treatment effect. This duration has been accepted as usually suitable for proof of concept studies in chronic pain conditions. The washout period of two weeks was based on preclinical pharmacodynamic data, as the pharmacokinetics of LAT8881 does not show a temporal association with its effect in pain models.

The power of the study was set at 90% to lessen the potential for a false negative outcome. To obtain this statistical power with a pragmatic sample size, the study was designed with two arms only (LAT8881 60 mg/day or placebo). Standard randomisation and double-blinding procedures are applied to ensure the validity of the study.

The efficacy outcome measures in this trial are based on those recommended by international consensus¹⁶ and are described in Section 10.5.

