All subjects will take their second Day 77 IMP dose in the evening. They will be asked to discontinue their IMP after taking the Day 77 evening dose.

End of Study (Day 91)

At the end of study visit, weight, vital signs, a targeted physical examination, concomitant medications and adverse events will be recorded. Blood and urine samples will be taken for safety analysis.

Early withdrawal

Subjects who withdraw early will be asked to attend an end of study visit. This visit should be scheduled approximately two weeks after the last dose was taken.

Statistical Analysis

With a total sample size of 44 evaluable subjects there is 90% power to demonstrate a statistically significant difference in the mean change from baseline NPRS for the active treatment compared with placebo of at least 1 unit. This assumes that the standard deviation of the change from baseline NPRS is 2, the correlation between active and placebo responses within a subject is 0.5 and there is a 2-sided test at the 5% level of significance. Assuming a 20% dropout rate, it is aimed to enrol at least 55 subjects to obtain 44 evaluable subjects.

The number of subjects within each treatment group is also sufficient to show a statistically significant change from baseline of 2 or more points on the NPRS.

The primary efficacy endpoint is the change from baseline mean NPRS score to the end of treatment mean NPRS score after LAT8881, compared with the change from baseline after placebo treatment. This will be analysed in the per protocol (PP) population, which will be defined in a statistical analysis plan (SAP) before database lock. The PP will be based on the duration of IMP treatment and protocol deviations.

Mixed effects regression models will be used to compare the absolute and percentage changes from baseline to the end of each treatment for the mean NPRS scores. The models will have fixed effects for period and treatment. Baseline mean pain score within each period by treatment combination will be included as a covariate. A random effect for subject will be included to capture the repeated measures nature of the design.

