6.1 Inclusion criteria

Subjects must meet the following criteria to be entered into the study:

1. Clinical diagnosis of post herpetic neuralgia, with pain persisting for at least 3 months after the onset of herpes zoster rash

OR

- 2. Clinical diagnosis of distal painful polyneuropathy due to Type I or Type II diabetes mellitus with:
 - a) symmetrical, bilateral pain in the lower extremities for at least 3 months and
 - b) diabetes under control for at least 3 months prior to randomisation, as indicated by a glycated haemoglobin level (HbA1c) of ≤ 11% (97 mmol/mol) and on a stable dose of insulin or oral diabetic medication for 3 months prior to screening, and
 - c) no change in diabetic medication planned for the duration of the study
- Positive sensory symptoms (mechanical or thermal) associated with neuropathic pain, confirmed by:
 - a) painDETECT Questionnaire (PD-Q) and
 - b) Clinical assessment, showing signs of neuropathic pain in either a dermatomal (PHN) or distal symmetrical distribution (DPN)
- 4. Aged 18 to 75 years
- 5. Subjects must be sufficiently competent in English to understand the purposes and risks of the study and able to give voluntary written informed consent to participate in the study
- 6. Willing and able to comply with all study procedures
- 7. Completion of at least five NPRS scores during the week preceding randomisation
- 8. An average daily pain score on the NPRS of at least 4 and no more than 8 in the last five diary entries before randomisation
- 9. No more than one score on the NPRS of 9 or more, and no more than one score of 2 or less, in the last five diary entries before randomisation
- 10. Females of child bearing potential must have a negative pregnancy test at Visit 1 (Screening) and at Visit 2 (Day 1) prior to administration of IMP
- 11. Female subjects must be:
 - a) of non child-bearing potential [surgically sterilised or post–menopausal (12 months with no menses without alternative medical cause)] OR
 - not pregnant, breast feeding or planning to become pregnant AND willing to comply with the medically acceptable contraceptive requirements of the study from Screening to at least 28 days after the last IMP administration

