13.2 Sample size

The sample size estimation is based on the following assumptions:

- Power of 90%
- The mean change from baseline NPRS for the active treatment compared with placebo is at least
 1 unit
- Standard deviation of the change from baseline in NPRS pain score is 2
- Correlation between active and placebo response is 0.5
- The test is two sided
- The dropout rate is 20%

The number of subjects within each treatment group is also sufficient to show a statistically significant change from baseline of 2 or more points on the NPRS.

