4.2 Sample Size Justification

It is planned to have 44 subjects complete the study. Assuming a 20% dropout, 55 subjects will be recruited. If the dropout rate is higher than 20%, additional subjects (up to 60 in total) may be recruited at the sponsor's discretion to ensure 44 subjects complete the study.

The sample size estimation is based on the following assumptions:

- *Power of 90%*
- *The mean change from baseline NPRS for the active treatment compared with placebo is at least 1 unit*
- *Standard deviation of the change from baseline in NPRS pain score is 2*
- *Correlation between active and placebo response is 0.5*
- *The test is two sided*
- *The dropout rate is 20%*

The number of subjects within each treatment group is also sufficient to show a statistically significant change from baseline of 2 or more points on the NPRS.

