11.6.2.2 Responder analysis

Number and percentage of subjects achieving $\geq 30\%$ and $\geq 50\%$ reduction in NPRS mean scores at the end of each treatment period (week 4) will be summarized. Proportions of responders will be compared between LAT8881 vs. Placebo across study periods using McNemar's test. P-values for testing the null hypothesis that there is no difference between LAT8881 and placebo will be reported.

```
proc freq data = ;  
table  
<responder>*<treatment>;  
exact mcnem; weight  
<subject>;  
run;
```

All analyses mentioned above will be repeated for Per-Protocol and FAS Populations.

In DDP: Table 14.2.3.1 to 14.2.3.2

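### The added McNemar responder test ignores period, and the SAP does not say whether it or the period-adjusted logistic model governs

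*Protocol*

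**What the plan says.** - **Design premise.** Protocol 5.2: "Because the pain is chronic, without a period effect, and treatment is symptomatic rather than curative, a crossover study is considered appropriate".
- **Entry on pain score.** Protocol 6.1, criterion 8, requires "An average daily pain score on the NPRS of at least 4 and no more than 8 in the last five diary entries before randomisation". Criterion 9 limits extreme scores, high and low, in the same five entries. Those ratings also form the Period 1 baseline (Protocol 9.1, SAP 10.12.2). At Day 50 the diary is reviewed (Protocol 8.6.1), but no pain-score threshold applies.
- **Responder test without period.** SAP 11.6.2.2: "Proportions of responders will be compared between LAT8881 vs. Placebo across study periods using" McNemar's test. It covers both thresholds in the per-protocol and full analysis sets. SAP 12 lists it as an addition to the protocol's analyses.
- **Responder model with period.** SAP 11.6.2.2.1 fits a mixed effects logistic model with period and treatment to the same two thresholds in the same two populations. Protocol 13.5.1 had already planned such a model.
- **Other NPRS treatment comparisons.** Absolute change (SAP 11.6.1.2), percentage change (11.6.2.1) and maximum reduction (11.6.2.3.1) all carry a period term.
- **Precedence.** None is stated between the two responder p-values. SAP 8.3 asks for caution with tests beyond the primary one.

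**The concern.** McNemar's test compares each subject's response on LAT8881 with the same subject's response on placebo and pools the two sequences. It is neutral to period only if response does not differ by period, or if the two sequences contribute equal numbers of complete pairs.

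Neither condition is assured. The Period 1 reference value is selected and the Period 2 reference is not, so regression to the mean can make the periods differ. The plan expects 20% dropout (Protocol 13.2), does not replace withdrawals (Protocol 5.8) and sets per-protocol membership separately by period (SAP 9.2). The complete pairs may therefore be unbalanced even if randomisation was balanced.

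At stake is the reading of two secondary endpoints. Each will have two p-values, one adjusted for period and one not, and no rule for choosing if they disagree.

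**Working it through.** **1. The plan's own figure.** The synopsis states "With a total sample size of 44 evaluable subjects there is 90% power", where "there is a 2-sided test at the 5% level of significance". The other inputs are "The mean change from baseline NPRS for the active treatment compared with placebo is at least 1 unit" (SAP 4.2), "Standard deviation of the change from baseline in NPRS pain score is 2" and "Correlation between active and placebo response is 0.5" (Protocol 13.2).
- SD of the within-subject difference = sqrt(2 × 2² × (1 - 0.5)) = 2.
- Normal approximation: n = (1.960 + 1.282)² × 2² / 1² = 42.03. The paired t-test at n = 44 gives power 0.900.
- Enrolment: 44 / 0.8 = 55.

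The figures reproduce. They concern the mean change; the plan states no power for responders. N = 44 is used below.

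**2. Shift in the McNemar contrast.** Let n1 subjects take LAT8881 first and n2 take placebo first, with period response rates p1 and p2 and no treatment effect.
- Expected responders on LAT8881: n1·p1 + n2·p2.
- Expected responders on placebo: n1·p2 + n2·p1.
- Difference in rates: (n1 - n2)/(n1 + n2) × (p1 - p2).

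This is zero if either factor is zero. Half the difference between sequences in mean Period 1 minus Period 2 response removes p1 - p2 whatever the split.

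**3. How large a period gap could entry selection cause?** The documents give no responder rates by period, so this was simulated. Assumptions: between-subject SD 1.5, week-to-week SD 1.0 or 1.5, day-to-day SD 0.8, criteria 8 and 9 applied to the first baseline, and a true drop of 0 or 1 point in each period.

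| Assumed screened mean NPRS | Period 1 minus Period 2, 30% responders |
|---|---|
| 4 | +6 to +11 points |
| 5 | +3 to +5 points |
| 6 | about 0 |
| 7 | -1 to -4 points |

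For 50% responders the gap ran from about -1 to +8 points.

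**4. Resulting shift.** Sequence sizes are not in the readable text, so the splits are assumed.

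| Split of 44 | 7-point gap | 11-point gap |
|---|---|---|
| 22:22 | 0 | 0 |
| 24:20 | 4/44 × 7 = 0.6 | 4/44 × 11 = 1.0 |
| 26:18 | 8/44 × 7 = 1.3 | 8/44 × 11 = 2.0 |
| 30:14 | 16/44 × 7 = 2.5 | 16/44 × 11 = 4.0 |

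One subject in 44 is 2.3 points. Under unrestricted 1:1 randomisation of 44, the sequences would differ by 4 or more with probability 0.65, by 8 or more with 0.29, and by 12 or more with 0.10. A restricted scheme would give less imbalance at randomisation.

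**5. Type I error.** Exact McNemar was enumerated at N = 44 with an assumed latent within-subject correlation of 0.5. With no period effect it is 0.025. With rates of 35% and 25%, a 10-point gap, it is 0.024 at 24:20, 0.027 at 26:18 and 0.037 at 30:14. Among the cases tried, it passed 0.05 only with a gap of 15 points or more at 30:14, or of 30 points at 28:16.

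**6. Power with equal sequences.** Simulated at 22:22 with a subject logit SD of 1.5 and a log odds ratio of 1.5. With period rates of 40% and 15%, McNemar had 57% to 59% power and Prescott's test 66%. With no period effect the figures were 71% and 69%. The 25-point gap is an illustration, well beyond what step 3 attributes to entry selection.

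**The case against.** The strongest reply is that the plan already holds the remedy. The period-adjusted logistic model covers both thresholds in both populations and was in the protocol before McNemar was added. These are secondary endpoints in a Phase IIa study, SAP 8.3 asks for caution, the likely shift is under one subject's worth at modest imbalance, and no false-positive problem appears at plausible settings. All of that stands, and it makes this a minor point. It does not settle which p-value governs.

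A reader might infer more, in three ways that the documents do not support.
- **That the responder comparisons as a whole are distorted once the sequences differ in size.** Only McNemar is exposed, and unequal sizes do nothing without a real period effect.
- **That entry selection must favour Period 1.** The 4-to-8 window is two-sided and criterion 9 limits both tails. Step 3 gives a gap near zero at a screened mean of 6 and a reversed one at 7.
- **That the premise in Protocol 5.2 undermines the main result.** That sentence defends the choice of a crossover. The primary model includes period in both documents, and nothing ties the sentence to the choice of McNemar.

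**Conclusion.** The concern holds for one added test. McNemar in SAP 11.6.2.2 takes no account of period, unlike the other LAT8881-placebo NPRS analyses, and the SAP does not rank it against the logistic model.

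Its responder difference is shifted only when a period effect and unequal sequences occur together. The shift is about 0.6 points at 24:20 and 1.3 points at 26:18 for an assumed 7-point gap, and about 1 and 2 points for an 11-point gap. Exact type I error remains below 5% at those splits. With equal sequences there is no shift, but a period effect lowers McNemar's power.

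These sizes rest on assumed pain distributions, response rates and sequence splits. Neither a period effect nor an imbalance is shown in the documents.

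**What to change.** In SAP 11.6.2.2, replace McNemar with a period-adjusted paired test by randomised sequence (Mainland-Gart or Prescott), or drop it. Add one sentence naming the responder test of record: either the planned logistic model or the replacement test. If the paired test is kept, report with it the period-adjusted responder difference from step 2 and its 95% CI.

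The code needs attention in any case. The McNemar code tabulates responder by treatment and weights by subject, which is not the paired table the test requires. If the logistic model is chosen, its RANDOM statement as printed names no effect. The model also omits the baseline covariate that Protocol 13.5.1 implies by carrying over the primary model's terms. Restore the covariate or explain the omission.

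The cost is a few lines of SAP text and code, and about 2 points of power (71% against 69% in step 6) if there is no period effect. The premise in Protocol 5.2 needs at most softer wording; changing it alters no analysis.
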